## 11 STUDY POPULATION

### 11.1 Inclusion Criteria

A subject will be eligible for inclusion in this study if all the following criteria apply:

1. Histologically-confirmed non muscle-invasive urothelial carcinoma (transitional cell carcinoma) of the bladder as follows:
  - CIS (with or without papillary disease) OR
  - Any grade T1 papillary disease OR
  - High-grade Ta papillary disease

based on a biopsy within 8 weeks of the initial dose of study treatment. If multiple bladder biopsies are required to confirm eligibility, the last bladder biopsy to the initial dose of study treatment must be within 8 weeks. This diagnosis must be confirmed by the independent central pathology reviewer prior to subject enrollment.

A subject with persistent T1 disease on the second (i.e., restaging) TURBT (see **Section 10.1**) may be enrolled in this study only if the investigator documents the subject declines cystectomy.

2. Subjects must have received adequate BCG treatment defined as at least 2 courses of BCG, i.e., at least one induction and one maintenance course or at least 2 induction courses. The initial induction course must be at least 5 treatments within a 7-week period. The second course (induction or maintenance) must be at least 2 treatments within a 6-week period. The “5+2” doses of BCG must be given within approximately 1 year (i.e., the start of one course to start of the second course within 12 months  $\pm$ 1 month) and for the same disease episode for which the subject is enrolling. Treatment must be considered “full-dose” BCG (see **Section 10**). If additional doses or courses of BCG above the minimum “5+2” are given, these do not have to be within the same approximate 12-month timeframe.

Subjects who were unable to receive at least 5 doses of BCG in a first course and at least 2 doses of BCG in a second course due to intolerance are not eligible.

Subjects who began their initial course of BCG with “full-dose” BCG and required dose-reductions due to adverse events but are still able to tolerate at least “5+2” doses of BCG are considered to meet the requirement for “adequate BCG.” Subjects who received less than “full dose” BCG (e.g., 1/3rd dosing) as a standard regimen and not due to dose reductions because of AEs are not eligible.

The BCG may have been given in combination with interferon. When BCG is given simultaneously in combination with interferon, 1/3rd dosing of BCG is acceptable.

3. The subject’s disease is refractory or has relapsed following adequate BCG treatment. Refractory disease is defined as disease which persists at the first evaluation following adequate BCG. Relapsed disease is defined as having a complete response to adequate BCG but recurs at a subsequent evaluation.

Subjects will enroll into one of three cohorts based on their type of disease and the time to refractory/relapsed disease following their last dose of BCG as follows:

- Cohort 1: Subjects with CIS with or without associated papillary disease whose disease is determined to be refractory or relapsed within 6 months of the last dose of adequate BCG treatment.
- Cohort 2: Subjects with CIS with or without associated papillary disease whose disease is determined to be refractory or relapsed more than 6 months but within 11 months of the last dose of adequate BCG treatment.
- Cohort 3: Subjects with high-grade Ta or any grade T1 papillary disease (without CIS) whose disease is determined to be refractory or relapsed within 6 months of the last dose of adequate BCG treatment.

For eligibility and cohort assignment: 6 months is defined as 30 weeks i.e., 26 weeks (6 months) plus an additional 4 weeks to accommodate scheduling variations and for diagnostic work-up and 11 months is defined as 50 weeks i.e., 48 weeks (11 months) plus an additional 2 weeks to accommodate scheduling variations and for diagnostic work-up.

For subjects enrolling in Cohort 2: The investigator documents he/she would not treat the subject with additional BCG at the time of study entry.

4. Male or non-pregnant, non-breastfeeding female, age 18 years or older at date of consent.
5. All women of childbearing potential (WOCBP) must have a negative pregnancy test within 7 days of the first dose of study therapy. A woman is not of childbearing potential if she has undergone surgical sterilization (bilateral tubal ligation, total hysterectomy, or bilateral oophorectomy) or if she is  $\geq 55$  years of age and has had no menstrual bleeding of any kind including menstrual period, irregular bleeding, spotting, etc., for at least 12 months and there is no other cause of amenorrhea (e.g., hormonal therapy, prior chemotherapy).
6. All sexually active subjects agree to use barrier contraception (i.e., condoms) while receiving study treatment and for 120 days following their last dose of study treatment. WOCBP and males whose sexual partners are WOCBP agree to use barrier contraception and a second form of contraception while receiving study treatment and for 120 days following their last dose of study treatment.
7. Karnofsky performance status  $\geq 60$  ([Appendix 1](#)).
8. Adequate organ function, as defined by the following criteria:
  - a. Serum aspartate aminotransferase (AST) and alanine aminotransferase (ALT)  $\leq 3.0 \times$  upper limit of normal (ULN);
  - b. Total serum bilirubin  $\leq 1.5 \times$  ULN (CTCAE Grade  $\leq 1$ );
  - c. Serum creatinine  $\leq 1.5 \times$  ULN; or a creatinine clearance  $\geq 40$  mL/min;
  - d. Hemoglobin  $\geq 8.0$  g/dL;
  - e. Absolute neutrophil count  $\geq 1500/\text{mm}^3$ ;
  - f. Platelets  $\geq 75,000/\text{mm}^3$ .
9. Ability to understand and sign an Independent Ethics Committee- or Institutional Review Board-approved informed consent document indicating that the subject (or legally acceptable representative) has been informed of all aspects of the trial and is willing and able to comply with scheduled visits, treatment plan, laboratory tests, and other study procedures. The informed consent document must be signed prior to the subject undergoing tests or

procedures solely for determining study eligibility and prior to receiving any protocol treatment.

## 11.2 Exclusion Criteria

A subject will not be eligible for participation if any one or more of the following criteria apply:

1. The subject is pregnant or breastfeeding.
2. Evidence of urethral or upper tract transitional cell carcinoma (TCC) within the past 2 years.  
Subjects with T1 disease must have no evidence of upper or lower tract disease or a more advanced stage of disease by CT urogram or MRI urogram of the abdomen and pelvis performed within 8 weeks of the first dose of study treatment. If intravenous contrast is contraindicated, retrograde ureteropyelography, or CT or MRI without intravenous contrast may be performed.
3. Subjects with hydronephrosis, except for those subjects where hydronephrosis has been longstanding (i.e., predates the diagnosis of the CIS, Ta or T1 by more than 2 years) and diagnostic evaluation at screening shows no evidence of tumor. Subjects with hydronephrosis that is unequivocally unrelated to upper tract malignancy may be considered eligible with Sponsor approval.
4. Any intravesicular or other chemotherapy treatment within 2 weeks or any investigational agent within 4 weeks prior to the initial dose of study drug.
5. History of recurrent severe urinary tract infections (UTIs) per investigator judgment.  
Subjects with a current UTI requiring antibiotic treatment may defer the initiation of Vicinium treatment on Day 1 until resolution of the UTI (even if this extends the screening period requirements to start of Vicinium treatment).
6. Active, uncontrolled impairment of the urogenital, renal, hepatobiliary, cardiovascular, gastrointestinal, neurologic or hematopoietic systems which, in the opinion of the Investigator, would predispose the subject to the development of complications from the administration of intravesical therapy and/or general anesthesia.
7. The subject has a diagnosis of another malignancy within 2 years before the first dose of study treatment, except for superficial skin cancer or localized solid tumors deemed cured by surgery and not treated with systemic anticancer therapy and not expected to require anticancer therapy in the next 2 years i.e., while the subject may be taking study treatment. However, subjects with low-risk prostate cancer, e.g.:
  - Clinically localized disease ( $\leq$ T2a) and
  - Gleason score 6 (3+3) and
  - Serum PSA  $<10$  ng/mLundergoing active surveillance may be enrolled with agreement of the sponsor.
8. A QTc interval of  $>470$  msec by the Fridericia formula (QTcF), at the Screening ECG. If the subject's QTcF is  $>470$  msec on the initial ECG, a total of 3 ECGs should be obtained at least 3 minutes apart and all within 30 minutes. The average of the 3 QTcF's will be used to determine eligibility. Known or suspected causes of prolonged QTc can be treated (e.g., hypocalcemia, hypokalemia, hypomagnesemia) and the ECGs may be repeated. If the subject initiates treatment with a drug known to prolong the QTc during the Screening period after the initial

Screening ECGs were obtained, the Screening ECGs must be repeated once the new drug has reached steady state to ensure the average QTcF remains  $\leq$ 470 msec. For subject's whose heart rate is  $<60$  bpm, the Bazett correction formula (QTcB) may be used.

9. Subjects who, in the opinion of the Investigator, cannot tolerate intravesical administration or intravesical surgical manipulation (cystoscopy, biopsy) due to the presence of serious comorbid condition(s) (e.g., uncontrolled cardiac or respiratory disorders).
10. Local or severe allergy to any components of the drug regimen.

### **11.3 Study Withdrawal Criteria**

Subjects are free to withdraw from treatment or from any further participation in the study (i.e., withdraw consent) at any time and without prejudice to further treatment. The Investigator should discuss with the subject if they want to withdraw from further treatment only (i.e., additional data will be collected) or from all further study participation at which time no data will be collected for the subject. The investigator must withdraw a subject from all further study participation if that subject withdraws consent. No additional evaluations will be done or data collected for subjects who withdraw consent. All subjects withdrawing from further study treatment should have Post-Treatment evaluation 30 – 37 days after the last dose of study treatment and receive follow up disease evaluation (every 3 months ([Section 10.6](#)) and until a protocol-defined event as well as be contacted for data secondary endpoint (PFS, OS). The reasons and details relevant to subject withdrawal must be recorded in the case report form (CRF). The Investigator must notify the Medical Monitor if a subject is withdrawn from the study.

Subjects must be withdrawn from study drug for any of the following reasons:

- Withdrawal of informed consent
- Pregnancy ([Section 12.5](#))
- Treatment failure ([Section 14.2](#))
- Documented extravesical (i.e., upper or lower tract) urothelial carcinoma
- Development of a second malignancy that requires systemic therapy
- Cystectomy
- Unacceptable toxicity
- Persistent non-compliance with the protocol requirements
- Treating physician / study Investigator concludes that it would be in the subject's best interest
- Intercurrent illness that, in the judgment of the Investigator, may affect assessments of clinical status to a significant degree, and that requires discontinuation of study drug.
- Sponsor terminates the study.

Subjects may be considered withdrawn if they fail to return for visits, or become lost to follow-up for any other reason. Every attempt should be made to re-establish contact for subjects who are lost to follow-up (i.e., those subjects whose status is unclear because they fail to appear for study visits without stating an intention to withdraw). The Investigator should undertake appropriate due diligence and document steps taken to contact the subject (e.g., dates of telephone calls, registered letters).

## 12 TREATMENT

### 12.1 Study Drug Administration

Subjects will receive study drug treatments twice weekly (BIW) for 6 weeks and once weekly for 6 weeks during the Induction Phase, and then enter the Maintenance Phase, if eligible ([Table 5](#)).

**Table 5:** Treatments

Study Phase	Treatment Regimen
Induction Phase (Weeks 1-12)	One intravesical dose of Vicinium 30 mg in 50 mL of saline instilled twice weekly (BIW) for 6 weeks followed by once weekly for 6 weeks, for a total of 12 weeks. The twice weekly doses are to be administered at least 48 hours apart (and no more than 2 doses may be administered within a calendar week, i.e., within a Sunday through Saturday period.) As an example, while a Monday/Thursday or Tuesday/Friday would be optimal, a Monday/Wednesday or a Tuesday/Thursday dosing schedule could be used. There will be a total of 18 doses over the 12-week period of the Induction Phase.
Maintenance Phase (up to Week 104)	One intravesical dose of Vicinium 30 mg in 50 mL saline instilled once every other week, for up to 24 months (Week 104) from the start of the Induction Phase.

To reduce urine flow during the instillation and dwell of Vicinium in the bladder, subjects will be asked to refrain from drinking any liquids beginning 2 hours prior to study drug instillation through completion of the 2-hour time period during which drug is held in the bladder. Immediately prior to bladder catheter insertion, subjects will empty their bladder. Appropriate study personnel will then insert a catheter into the bladder, and the bladder will be drained.

An appropriate local anesthetic and sterile lubricant may be used at the time of catheterization. In addition, an antibiotic may be given at the discretion of the Investigator. The use of any medications must be recorded on the subject CRF.

#### Vicinium Administration

Vicinium 30 mg in 50 mL of saline will be instilled through a catheter into the bladder. Subjects will be instructed to hold study drug in the bladder for 2 hours, and asked to refrain from fluid intake to reduce urine flow during this period. After complete administration of the Vicinium dose, the catheter may be clamped and remain in for the 2-hour dwell time, or may be removed, per the discretion of the investigator. Subjects will be required, when physically possible, to be upright (sitting or standing), prone, supine, and in the left and right lateral decubitus positions, for at least 15 minutes each, in any order. If physically unable, this should be recorded in the CRF. At the end of 2-hour period, the catheter will be unclamped and the bladder will be drained (if the catheter remained in place) or the subject will void to empty the bladder.

## **12.2 Concomitant Medications**

In this clinical study, Vicinium will be administered as a monotherapy. Beginning 2 weeks prior to the initial dose of study drug and throughout the time the subject is receiving Vicinium treatment, no other anti-cancer therapies that could affect the disease under study, including radiation therapy, immunotherapy, vaccine therapy, biological therapy, or gene-based therapies will be permitted with the exception that subjects who enter the study with low-risk prostate cancer undergoing active surveillance who, while on study then require androgen-deprivation therapy may be permitted to remain on Vicinium treatment with Sponsor permission. Additionally, no other investigational agent is permitted within 4 weeks before the start of study drug and throughout the time the subject is receiving Vicinium treatment.

Any other medication that is considered necessary for the well-being of the subject, and that is not expected to interfere with the evaluation of the study drug, may be given at the discretion of the Investigator.

All concomitant therapies taken from Screening until the subject has a protocol-defined event must be recorded in the subject's medical record and transcribed to the CRF.

## **12.3 Treatment Compliance**

Study drug administration will take place at the study site under supervision of the Investigator or other authorized clinic staff.

## **12.4 Randomization and Blinding**

This is an open-label, non-randomized study.

## **12.5 Pregnancy Occurring During the Clinical Trial**

It is the responsibility of the Investigator to report to the study Medical Monitor within 24 hours of learning of its occurrence any pregnancy in a subject or in the female partner of a male subject that occurs during the study or within 120 days of the last dose of study drug. If the subject is pregnant, study drug must be discontinued. If the female partner of a male subject is pregnant, the subject may continue on treatment. Barrier contraception must be used or abstinence must be practiced if the male subject continues on treatment. The pregnancy should not be recorded as an adverse event (AE); however, the Investigator will be required to complete a Pregnancy Notification form.

The pregnancy should be followed to determine outcome, including spontaneous or voluntary discontinuation, and the presence of any congenital abnormalities, or maternal and/or newborn complications. Pregnancy follow-up should be recorded on the Pregnancy Follow-up form and reported by the Investigator to the study Medical Monitor. If the pregnancy continues to term, the outcome (health of infant up to a minimum of 6 months of age) must also be reported to the Sponsor or their representative. For any maternal and/or newborn complications, the Investigator should assess if there is a possible relationship to the study drug and evaluate whether it should be reported as an AE or serious adverse event (SAE) ([Section 15.3](#)). The presence of congenital anomalies must be reported as an SAE.

## 12.6 Study Drug Interruptions

- In subjects who develop low-grade papillary disease while on treatment, study drug must be interrupted for a minimum of 2 weeks following tumor removal before restarting Vicinium treatment.
- The following criteria will be used for holding Vicinium dosing based on serum creatinine and calculations or measured creatinine clearance:

Baseline Creatinine	Criteria for Holding Vicinium Treatment*	
	Serum Creatinine	Creatinine Clearance
<1.0 mg/dL or <88 µmol/L	>1.5 mg/dL or >133 µmol/L	<40 mL/min or a decrease of 25% from baseline
≥1.0 mg/dL or ≥88 µmol/L	Increase to >1.5x baseline value	<40 mL/min or a decrease of 25% from baseline

\*Vicinium dosing should be held if **either** the serum creatinine or the creatinine clearance criteria, as defined in this table, are met.

The investigator should contact the Sponsor for these changes in renal function and the subject should be evaluated for the etiology of these changes. Vicinium treatment may be resumed upon improvement or stabilization at creatinine of  $\leq 2x$  baseline or  $\leq 2x$  ULN and with Sponsor agreement.

- Vicinium dosing must be held for any subject whose AST or ALT doubles from their baseline value and is  $\geq 2x$  ULN; OR for a bilirubin  $\geq 2$  mg/dL ( $\geq 34$  µmol/L). The investigator should contact the Sponsor for these changes in liver function tests and the subject should be evaluated for the etiology of these changes. Vicinium treatment may be resumed upon improvement or stabilization of AST and ALT of  $\leq 2x$  baseline or  $\leq 2x$  ULN; OR for a bilirubin  $\leq 2$  mg/dL ( $\leq 34$  µmol/L) and with Sponsor agreement.
- The investigator should consider holding Vicinium treatment for patients with a clinically significant UTI requiring antibiotic therapy until improvement
- Study drug administration must be postponed if a subject develops any Grade 3 or greater adverse event as defined using the NCI-CTCAE version 4.03 ([http://evs.nci.nih.gov/ftp1/CTCAE/CTCAE\\_4.03\\_2010-06-14\\_QuickReference\\_8.5x11.pdf](http://evs.nci.nih.gov/ftp1/CTCAE/CTCAE_4.03_2010-06-14_QuickReference_8.5x11.pdf)) considered related to Vicinium treatment. Study treatment may resume when the AE returns to  $\leq$  Grade 1 or baseline or sooner **if there is agreement between the investigator and the sponsor**. Study treatment may be postponed at the discretion of the investigator for unrelated AEs, if this is considered in the best interest of the subject. If the causal relationship between Vicinium and an AE is initially uncertain, study drug should be interrupted until that determination is made. Also study treatment may be postponed for lower grade AEs at the investigator discretion if considered in the best interest of the subject.

Missed doses of Vicinium due to interruption of dosing for adverse events should not be made up. In the Maintenance Phase, dosing should be restarted as soon as there is AE resolution i.e., treatment should not be postponed longer in order to align with the initial every-other-week schedule.

If study treatment is postponed longer than 3 weeks, this should be discussed with the Sponsor to determine if the subject should remain on treatment.

The reasons and details relevant to the subject postponement and/or discontinuation of study treatment must be recorded on the CRF. The Investigator must notify the Medical Monitor if study treatment is discontinued.

Subjects discontinuing from study treatment will not be replaced.

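### Inclusion 8c admits subjects with creatinine clearance below 40 mL/min who already meet the Section 12.6 renal hold, and the restart text overlaps the hold without saying which then governs

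*Protocol*

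**What the plan says.** **Eligibility.** Protocol Section 11.1, criterion 8c, and the matching Synopsis item set two renal conditions as alternatives: creatinine up to 1.5 times "ULN; or a creatinine clearance $\geq 40$ mL/min". Meeting one is sufficient.

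**Hold.** The table in Protocol Section 12.6 has two rows by baseline creatinine.
- Baseline below 1.0 mg/dL: the serum limit is ">1.5 mg/dL or >133 µmol/L".
- Baseline 1.0 mg/dL or above: the serum limit is "Increase to >1.5x baseline value".
- Both rows: the clearance limit is "<40 mL/min or a decrease of 25% from baseline".

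The footnote says dosing should be held if either of "the serum creatinine or the creatinine clearance criteria, as defined in this table, are met", with the word for either in bold. The table makes no exception for a subject who entered below 40 mL/min.

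**Restart.** The same section has the site contact the Sponsor and look for the cause. It then allows dosing to resume on "improvement or stabilization at creatinine of $\leq 2x$ baseline or $\leq 2x$ ULN and with Sponsor agreement". Clearance is not mentioned.

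**Analysis sets.** SAP Section 4.2 defines mITT by receipt of at least one dose. SAP Section 4.3 defines the primary efficacy population as the mITT subjects with CIS.

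**The concern.** Eligibility needs one of two renal measures to be acceptable. The hold needs only one of the same two to be unacceptable. With 40 mL/min as an absolute limit in both places, a subject can pass the first test and fail the second on the same baseline sample. The site then has no written instruction on whether to give the first dose.

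This is a renal safety rule, added in version 4.0 according to the summary of changes. It also reaches the analysis, because one dose decides whether a subject is in mITT. Sites that read the conflict differently would treat identical subjects differently at the door of the primary population.

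The restart text raises a second, softer question. Its ceilings are higher than the level that starts the hold, and it ignores one of the two measures that can start it. A subject may resume with Sponsor agreement while still meeting the hold table. The protocol does not say what the next chemistry review before a dose should then conclude.

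**Working it through.** The point concerns the logic of thresholds, so the plan has no power or sample-size figure to reproduce. The printed unit conversions agree: 1.0 x 88.4 = 88.4 and 1.5 x 88.4 = 132.6 µmol/L, against 88 and 133 in the table.

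**Step 1. Eligibility against hold at baseline.** Write S for creatinine, C for clearance and B for baseline creatinine.
- Eligible: S ≤ 1.5 x ULN or C ≥ 40.
- Serum hold: S > 1.5 mg/dL if B < 1.0; S > 1.5 x B if B ≥ 1.0.
- Clearance hold: C < 40, or a 25% fall from baseline.

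At a subject's own baseline S = B, so the serum hold cannot be met, and the fall in clearance is zero. Only the absolute limit C < 40 can trigger. Every subject with S ≤ 1.5 x ULN and C < 40 is therefore both eligible and on hold.

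Enumeration agrees. I took ULN of 1.0, 1.2 and 1.4 mg/dL (assumed, since the documents give none), creatinine of 1.0, 1.2 and 1.5 mg/dL, and clearance of 20, 30, 35, 39.9, 40 and 45 mL/min. All 3 x 3 x 4 = 36 combinations with clearance below 40 are eligible and meet the hold. None of the 18 at 40 or 45 does.

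**Step 2. Are such values plausible together?** Section 12.6 allows calculated or measured clearance but names no formula. I assume Cockcroft-Gault: (140 − age) x weight / (72 x S), times 0.85 for women.
- Woman, 80 years, 60 kg, 1.1 mg/dL: 60 x 60 / 79.2 x 0.85 = 38.6 mL/min. She passes on creatinine for any ULN of at least 1.1/1.5 = 0.73 mg/dL.
- Man, 85 years, 65 kg, 1.3 mg/dL: 55 x 65 / 93.6 = 38.2 mL/min. He passes for any ULN of at least 1.3/1.5 = 0.87 mg/dL.
- Man, 85 years, 60 kg, 1.1 mg/dL: 55 x 60 / 79.2 = 41.7 mL/min. He is not affected.

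These invented cases show that the conflict can occur, not how often it does.

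**Step 3. Hold against restart, serum limits (mg/dL).** The restart ceiling is the larger of 2 x B and 2 x ULN.

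| Baseline B | Hold above | Ceiling, ULN 1.0 | Ceiling, ULN 1.2 | Ceiling, ULN 1.4 |
|---|---|---|---|---|
| 0.8 | 1.5 | 2.0 | 2.4 | 2.8 |
| 1.0 | 1.5 | 2.0 | 2.4 | 2.8 |
| 1.2 | 1.8 | 2.4 | 2.4 | 2.8 |
| 1.5 | 2.25 | 3.0 | 3.0 | 3.0 |

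For B ≥ 1.0 the overlap runs from above 1.5 x B to 2 x B, or to 2 x ULN if that is larger. For B < 1.0 it runs from above 1.5 mg/dL to the larger of 2 x B and 2 x ULN. The multiples of 1.5 and 2 do not describe the second group: at B = 0.7 they give 1.05 to 1.4 mg/dL, all below the serum hold.

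**Step 4. Clearance in the restart rule.** A subject held only for clearance below 40, with unchanged creatinine, is at 1.0 x B and so already under the restart ceiling. If calculated clearance is inversely proportional to creatinine, with age and weight fixed, a 25% fall corresponds to 1/0.75 = 1.33 x B, which is also under 2 x B.

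**Step 5. Comparison with the liver rule.** In the same section, the AST/ALT hold needs a doubling from baseline and at least 2 x ULN; restart needs at most 2 x baseline or at most 2 x ULN. Apart from the boundary, one is the complement of the other. The renal limits are not built that way.

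**The case against.** The strongest defence is that Section 12.6 describes two stages: a sensitive trigger for review, then supervised resumption. Restart needs contact with the Sponsor, a search for the cause, a value that has improved or settled, and Sponsor agreement. The renal wording is that dosing should be held, where the liver rule says must. This stands against any claim that hold and restart flatly contradict each other, or that a restarted subject is bound to be held again. Re-triggering is an inference: the text neither requires it nor rules it out.

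It does not dispose of the eligibility conflict. The Sponsor route is worded for resuming treatment and fits poorly before a first dose. Exclusion 6 removes only active, uncontrolled renal impairment in the investigator's opinion, so stable low clearance can remain.

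One could also say that an interruption rule starts only after dosing has begun. The first on-treatment chemistry is then normally reviewed before the second dose of week 2, the fourth dose overall. A subject with unchanged clearance meets the hold there. On that reading the mITT consequence falls away, but the conflict is only postponed.

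Four stronger readings are tempting and not supported.
- That affected subjects always stay in the primary denominator: a subject never dosed is not in mITT.
- That doses missed under the hold are permanently lost: Section 12.6 says this of interruptions for adverse events, and an unchanged baseline clearance is not clearly one.
- That the SAP age split at 75 shows such subjects are expected: an age cut says nothing about weight, creatinine or clearance.
- That sites must either refuse an eligible subject or ignore the rule: contact with the Sponsor is a third course, though not one written for this case.

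**Conclusion.** The concern holds in two parts of unequal strength.

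The conflict between inclusion 8c and the 40 mL/min hold is wrong as written. It follows from the text alone, for any ULN and any clearance formula, and covers every subject who qualifies on creatinine with clearance below 40. Its effect on mITT and the primary efficacy population depends on sites applying the hold before dose 1, which the documents do not settle.

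The restart part is an ambiguity. The creatinine ranges overlap and clearance is absent from the restart text, but the stability and Sponsor-agreement conditions stand between the two rules. What is missing is a statement of whether the hold applies again after an agreed restart.

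The number of affected subjects cannot be derived from the documents. The worked cases rest on an assumed formula and the restart ceilings on an assumed ULN of 1.0 to 1.4 mg/dL. The point is worth correcting because it concerns a renal safety rule and who receives a first dose. It takes no position on which threshold is right.

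**What to change.** The sponsor should reconcile inclusion 8c (Section 11.1 and the Synopsis) with the hold table and restart text in Section 12.6, by protocol amendment or clarification letter. The same document should state whether the hold applies again at the next chemistry review before a dose, once a restart has been agreed, and should name the formula for calculated clearance. The rule and its values are for the sponsor's medical lead.

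The cost is a short document. No new tests are needed, since chemistry is already drawn and reviewed before dosing, and no sample-size or analysis change follows.
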